We will also explore the dosing of the intervention. Because the intervention is needs-based, FCGs will receive different levels (e.g. eSNAP only; eSNAP plus Caregiver Navigator sessions of differing length/frequency). We will first describe the different levels of intervention used. We will then test the relationship of FCG reported support, distress, and burden and the frequency and time spent engaging in intervention components using repeated measures multilevel modeling. We hypothesize that FCGs who report less support or more distress or burden at enrollment will engage more components of the intervention.

Key mechanisms from the conceptual model (Figure 1) will also be explored using data from all who used the intervention at any time. Planned analyses include describing FCG health care utilization, determining whether intervention components (e.g. eSNAP visualization and resource list/Caregiver Navigator referrals) predict FCG health care utilization, and testing the relationship between FCG health care utilization and FCG well-being. We will also use path analysis to test mediation models mapping FCG support, burden, and distress over time and to test parallel processing models to determine interdependent effects between FCG and patient. For example, we will test whether change in FCG distress is associated with change in patient distress. In addition to identifying key mechanisms of the intervention, these analyses also would contribute to the literature describing the experience of FCGs of patients with a primary brain tumor, secondary (metastatic) brain tumor, or leptomeningeal disease over time.

Qualitative analysis of FCG interviews will augment quantitative analysis. FCGs will be interviewed at 8 weeks about their caregiving experience, including what they liked about the intervention and what could be improved (See Appendix for draft interview guide). Interview audio recordings will be professionally transcribed verbatim. Transcripts will undergo content analysis using open and axial coding by 2 trained coders, led by [name], who has expertise in qualitative analysis.(Dingley et al., 2017; Ellington et al., 2017; Lai et al., 2018; Reblin, Birmingham, Kohlmann, & Graff, 2018; Reblin et al., 2015; Tabler et al., 2015) The goal of the analysis will be to identify aspects of the intervention FCGs found helpful and areas for improvement. Deeper analysis on select transcripts will be conducted to identify themes relevant to findings of the quantitative analysis and emergent themes regarding the caregiving experience.

The audio recordings and transcripts will be stored on secure, password-protected computer servers and will only be accessed by study team members. Audio recordings and transcripts will be retained for at least six years after the study is completed, after which they will be deleted from computer records.

5. Human Subjects Protection

Potential Risks:

There are a few potential risks to the participants. Participants may feel emotional distress when completing questionnaires or thinking about their social networks or caregiving experiences. There is also the possibility of loss of privacy or confidentiality.

Planned strategies for minimizing potential risks

Emotional Distress:

Participants may feel emotional distress when completing questionnaires or thinking about their social networks or caregiving experiences. Some participants may become distressed as a result of their experiences in caregiving. This level of distress is not likely to be more than would occur in daily life or as part of usual care. In the intervention condition (which waitlist control participants may receive after 8 weeks), the Caregiver Navigator will have training to counsel or refer any participant who feels distressed,

with support from the interdisciplinary team of investigators and consultants, as well as involvement of the neuro-oncology clinic staff. Part of the role of the Caregiver Navigator is to connect participants with other resources; this will include transitioning care to the neuro-oncology clinic social worker to minimize distress at the end of the study. This social worker is available to all patients and their families, including waitlist control participants, at any time during the patient's care. Emergency procedures, as outlined by Moffitt policy, will be in place should any psychiatric emergency arise. This includes the immediate contact of social work for a risk assessment if a participant is in extreme distress or expresses suicidality. A social worker is on call 24/7 and will make appropriate recommendations for follow-up care in collaboration with the medical team. Although this is likely to be very rare, all study personnel will be trained in these procedures.

Loss of Privacy or Confidentiality:

Precautions will be taken to protect the privacy of all participants contacted to be in the project and for those who participate. Only the study team will have access to participant research data and only trained staff with appropriate approvals will have access to patient medical records when provided consent to do so. All participants will be identified in study files by ID numbers. The study staff will maintain a separate password-protected file behind the Moffitt Cancer Center firewall linking participant IDs to names. Paper questionnaires will have participant IDs and will be stored in a locked file in the study office and entered into an electronic database. Digital audio-recordings will be made only with participant consent. All research data is stored on password-protected computers, secure online platform (REDCap) or in locked cabinets in the PI's office at the Moffitt Cancer Center. All Protected Health Information (e.g. participant names) and identifying data will be kept in a password-protected and encrypted computer or network drive specifically designed for protection of research participant confidentiality at the Moffitt Cancer Center. These systems and devices are all encrypted to protect the research data and participants' privacy. Signed consent forms and participant contact information are kept in password protected and encrypted electronic or physical files within the Moffitt Cancer Center and overseen by the PI. The collection of information about participants is limited to the amount necessary to achieve the aims of the research so that no unneeded information is being collected. Data shared among research team members will be kept confidential. In the course of Caregiver Navigation sessions, the navigator may ask permission to share relevant data with the patient's care team. Caregivers who choose to interact with the Caregiver Navigator or study team by email will be informed that correspondence may not be encrypted and that no PHI should be sent by email. The Caregiver Navigator will be extensively trained and will work closely with the neuro-oncology clinic staff; all effort will be made to support and reinforce information delivered by health care providers. All study staff will receive training in confidentiality safeguards, human subjects and HIPPA certification, research ethics and recruitment, retention and data collection methods and best practices. Throughout the study, periodic updates will be provided at project meetings.

1. Potential Benefits of Proposed research to participants and others

Participants will be told that benefits to participating in research are not guaranteed. Participants may find the eSNAP tool to be helpful in thinking about and organizing their social network resources. Participants may also find benefit in discussing their situation with the Caregiver Navigator and/or discovering or reengaging new and existing support resources. These services are over and above usual care. Although all family caregivers of patients have access to psychosocial care in the form of support groups and the clinic social worker, there is currently no systematic way to make direct referrals in usual care. The organizational exercise of using the eSNAP app, talking to the navigator, and/or using the social resources identified may improve support and reduce caregiver stress, which may in turn improve quality

of life. Participants may also feel good about participating in research with the goal of helping other family caregivers and improving the caregiving experience.

Potential benefits to society include development of an intervention to capitalize on existing social resources to reduce caregiver burden as well as improving stress and quality of life outcomes. This intervention, once developed and tested, may be adapted for use with other caregiving populations as well as other populations where visualizing social network resources or facilitating discussions about social network resources may be beneficial.

2. Importance of Knowledge to be Gained:

This proposal addresses the needs of family caregivers of patients with a primary brain tumor, secondary (metastatic) brain tumor, or leptomeningeal disease —a high-need population that is historically underserved and under-studied in research. Family caregivers, especially in this population, are in need of simple, cost-effective ways to reduce burden. However, the primary way to do this identified in the literature, facilitating family caregivers' engagement with their social networks, has not been widely implemented due to barriers in existing methods. We propose to reduce these barriers providing a web-based app to help caregivers organize and prime their existing social support resources, and by providing access to a Caregiver Navigator, who can help problem-solve and make arrangements or referrals. The findings of this study have the potential to inform future interventions with eSNAP and the development of caregiver navigation programs and improve family caregiver outcomes for neuro-oncology family caregivers as well as other groups in need of help harnessing existing social network resources.

6. References

Andresen, E. M., Vahle, V. J., & Lollar, D. (2001). Proxy reliability: health-related quality of life (HRQoL) measures for people with disability. *Quality of Life Research, 10*(7), 609-619.

Ankuda, C. K., Maust, D. T., Kabeto, M. U., McCammon, R. J., Langa, K. M., & Levine, D. A. (2017). Association Between Spousal Caregiver Well-Being and Care Recipient Healthcare Expenditures. *Journal of the American Geriatrics Society, 65*(10), 2220-2226. doi:10.1111/jgs.15039

Archbold, P. G., Stewart, B. J., Greenlick, M. R., & Harvath, T. (1990). Mutuality and preparedness as predictors of caregiver role strain. *Research In Nursing & Health, 13*(6), 375-384.

Baron, R. S., Cutrona, C. E., Hicklin, D., Russell, D. W., & Lubaroff, D. M. (1990). Social support and immune function among spouses of cancer patients. *Journal of Personality and Social Psychology, 59*(2), 344-352.

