Missing Data: Participants who do not submit data at F1 or who decline navigation will continue to be contacted at F2 to complete questionnaires (unless they withdraw from the study) for intent to treat analyses. We plan to begin recruitment early in the care trajectory and anticipate most patients will survive the 8-week study period and will be able to provide the limited amount of data we are collecting. The median survival time for patients with primary malignant brain tumor is 14.6 months.(National Brain Tumor Society) In the unlikely event patients no longer receive care in the neuro-oncology clinic at Moffitt (transition to palliative/hospice care, change providers, death) participants will not be dropped (unless they request to withdraw). Participants in the intervention condition will still have access to eSNAP (and the Navigator) if they wish, with the intent of allowing FCGs to use the intervention to help cope with the new phase of caregiving or bereavement. FCGs will still be asked to complete follow-up questionnaires. If a patient dies, the date of death will be noted, a bereavement card will be sent from the study team, and an abbreviated version of any further surveys will be administered focused on key outcome data for exploratory purposes.

Sample size justification: The analyses for Aims 1 & 2 focus on group differences in parametric variables. A power analysis for an independent-groups t-test with a medium effect size (Cohen's $d=0.5$) shows that a final sample of 160 (80 per group) would have Power $\geq .80$ with alpha=.05 and a two-tailed test. Based on our conservative recruitment and retention estimates, we plan to approach 300 FCGs and enroll 225 to achieve a final sample of 160 dyads completing the 8-week assessment for analyses of hypotheses. However, as the planned recruitment/retention rates are lower than what we achieved in our pilot, we may have a larger sample at F2, which will increase our power. Analyses for exploratory Aim 3 will

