Aim 2 is to assess the preliminary efficacy of interdependent effects of eSNAP + Navigator on patient well-being and health care utilization. We hypothesize that patients with FCGs in the intervention group will report greater well-being and less utilization of health care. The primary outcomes for this aim are (1) patient anxiety and depression scores as (inverse) measures of well-being, and (2) a set of measures for healthcare utilization: the presence of and number of unplanned outpatient visits, the presence of and number of unplanned hospitalizations, and the number of bed days of care in unplanned hospitalizations. For well-being, the simplest test of the hypothesis is an independent samples t-test. If preliminary analyses show that randomization was not fully successful, then linear regression will be used to assess differences between the intervention arms in the context of any potential confounds. For healthcare utilization, the distributions of the outcome variables are expected to warrant 2-stage and/or Poisson regression analyses to assess intervention differences.

Exploratory Aim 3 is to identify key intervention components using mixed methods to inform future intervention implementation. Our quantitative approach will first involve determining the **timing and dose effects of the intervention**. Between-groups GEE analyses will utilize the full dataset to determine if stronger effects of the intervention exist when the intervention is delivered at the first treatment planning appointment (intervention group) or 8 weeks later (waitlist participants who engage in the intervention). We will also analyze data collected from all participants at 6 months and 1 year. Although likely a smaller dataset with some selection bias, these data may provide insight into long term effects on FCG and patient well-being and an opportunity to capture patient hospitalization, a relatively rare but important downstream effect of FCG burden.

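### The single t-test power statement for Aims 1 and 2 does not cover the five healthcare utilization outcomes among Aim 2's seven primary outcomes

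*Combined protocol and SAP*

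**What the plan says.** Section 4 (Sample size justification) treats the two main aims together: "The analyses for Aims 1 & 2 focus on group differences in parametric variables". One calculation follows: "A power analysis for an independent-groups t-test with a medium effect size" (d = 0.5), from which "a final sample of 160 (80 per group) would have Power" of at least .80 "with alpha=.05 and a two-tailed test". No outcome is excepted.

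Section 4 (Aim 2) then lists the outcomes: "The primary outcomes for this aim are (1) patient anxiety and depression scores as (inverse) measures of well-being", and a second set on utilization: "the presence of and number of unplanned outpatient visits, the presence of and number of unplanned hospitalizations", plus bed days in unplanned hospitalizations. The scores are to be compared by t-test or linear regression. The second set is treated differently: "For healthcare utilization, the distributions of the outcome variables are expected to warrant 2-stage and/or Poisson regression analyses to assess intervention differences".

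Under Exploratory Aim 3, in a sentence about the 6-month and 1-year data, the plan refers to "patient hospitalization, a relatively rare but important downstream effect of FCG burden". Section 3a reports that those later assessments were discontinued after amendment V11. Neither the protocol nor the analysis section gives a rate, mean, dispersion, target ratio or power for any utilization outcome.

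**The concern.** A power figure belongs to one test, one effect measure and one type of outcome. Here a t-test figure for a standardized mean difference is attached to an aim in which most of the named primary outcomes are not means and will not be tested by a t-test. The mismatch is present at the planned 80 per group, so bringing the enrolment figures up to date would not remove it.

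Fewer unscheduled visits and hospitalizations form one of the two limbs of the Aim 2 hypothesis in Section 1. As the text stands, a non-significant utilization result could be reported as coming from a trial with at least .80 power, although the plan never established that for these outcomes.

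**Working it through.** **Inputs from the documents.** d = 0.5, two-sided alpha .05, 80 per group (Section 4, Sample size justification). 160 dyads enrolled and 15% attrition at each follow-up (Section 3b, Participants). About 2:1 intervention to waitlist (Section 3a). Completers at current enrolment: 160 × 0.85 = 136, or 91:45 after one loss; 160 × 0.85 × 0.85 = 115.6, about 116, or 77:39 after two.

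**Inputs that are assumptions.** All event risks, count means, dispersions and reductions below. The documents give none.

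**1. The plan's own figure.** Noncentrality = d / √(1/n₁ + 1/n₂) = 0.5 / √(2/80) = 3.16. The critical t on 158 df is 1.975. Power = 0.88, and 64 per group gives 0.80. The statement is correct for a scale score at 80:80.

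**2. Which outcomes it fits.**

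| Aim 2 primary outcome | Type | Planned analysis |
|---|---|---|
| Patient anxiety score | scale | t-test or linear regression |
| Patient depression score | scale | t-test or linear regression |
| Any unplanned outpatient visit | binary | 2-stage and/or Poisson |
| Number of unplanned outpatient visits | count | 2-stage and/or Poisson |
| Any unplanned hospitalization | binary | 2-stage and/or Poisson |
| Number of unplanned hospitalizations | count | 2-stage and/or Poisson |
| Bed days | count | 2-stage and/or Poisson |

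Two fit the calculation; five do not.

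**3. Binary outcomes, risk halved.** Power = Φ[(|p₁ − p₂| − 1.96·SE₀)/SE₁], where SE₀ = √[p̄(1 − p̄)(1/n₁ + 1/n₂)], p̄ is the size-weighted mean risk, and SE₁ = √[p₁(1 − p₁)/n₁ + p₂(1 − p₂)/n₂].

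Example, 20% to 10% at 80:80: SE₀ = √(0.15 × 0.85 × 0.025) = 0.0565; SE₁ = √(0.25/80) = 0.0559; (0.10 − 0.1107)/0.0559 = −0.19; power = .42.

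| Assumed control risk | 80:80 | 91:45 | 77:39 |
|---|---|---|---|
| 10% | .22 | .22 | .20 |
| 20% | .42 | .38 | .33 |
| 30% | .62 | .54 | .48 |
| 40% | .79 | .69 | .63 |
| 50% | .91 | .83 | .77 |

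Read the other way, .80 power at 80:80 needs a fall from 10% to about 0.3%, from 20% to about 5.4%, or from 30% to about 12%.

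**4. Count outcomes at 80:80.** SE(ln RR) = √[(1/μ + k)/n₁ + (1/(μ·RR) + k)/n₂], where μ is the control mean, RR the rate ratio and k the dispersion (k = 0 is Poisson). Power = Φ(|ln RR|/SE − 1.96).

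Example, μ = 0.3, RR = 0.5, k = 0: SE = √(3.333/80 + 6.667/80) = 0.354; 0.693/0.354 − 1.96 = 0.00; power = .50.

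| Assumed mean, reduction | k = 0 | k = 1 | k = 2 |
|---|---|---|---|
| 0.3, one third | .24 | .20 | .18 |
| 0.3, half | .50 | .43 | .38 |
| 1.0, half | .95 | .79 | .65 |

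Bed days are zero for anyone without an unplanned hospitalization, so a figure for them would also need an assumed length of stay. None is offered here.

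**5. Scale scores at current numbers, d = 0.5, t-test.** 107:53 (no attrition) gives 0.84; 91:45 gives 0.78; 77:39 gives 0.71.

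**The case against.** The case on the other side has four parts.

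- **Readers are already warned.** Section 4 (Effect of modified design) says differences may be harder to detect, and Sections 1 and 4 call Aim 2 an assessment of preliminary efficacy. This softens the harm. It does not cure the gap, because the warning is tied to the change in accrual and says nothing about outcome type.
- **The planned models already suit the data.** True: no analysis method, enrolment figure or data collection depends on the power sentence. This lowers the severity but leaves the sentence wrong in scope.
- **Events may be common.** This stands. A reader might infer that all five outcomes are rare and underpowered. The documents do not support that: only hospitalization is called relatively rare, and unplanned outpatient visits never are. At 80:80, halving a 50% risk gives .91 power, and halving a Poisson count of mean 1.0 gives .95.
- **A primary outcome need not have its own power calculation in a preliminary-efficacy study.** This also stands. A reader might conclude that the utilization measures should become secondary. That would change the endpoint hierarchy of a stated hypothesis after randomization has stopped, and could itself be criticized as outcome switching. The scope error does not require it.

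**Conclusion.** The power statement is wrong in scope as written. It claims at least .80 for Aims 1 and 2 without exception, while five of the seven Aim 2 primary outcomes lie outside the calculation. For those five, power is not established. It is low if events are uncommon: about .22 to .62 at 80:80 for control risks of 10 to 30% halved, and .18 to .50 for a count of mean 0.3 reduced by a third to a half. It approaches or passes .80 only for common events with large reductions. Every one of these figures rests on assumed rates, so they show a range and not the trial's actual power.

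Two stronger readings should be resisted. The t-test figure is not miscalculated; it reproduces at 0.88. Nor do the documents show that power is low for every utilization outcome, least of all for outpatient visits. The point should be fixed, but it does not threaten the conduct of the trial.

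**What to change.** **Section 4, Sample size justification.** Limit the power statement to the scale scores (caregiver burden, GAD-7, PHQ-8) and restate it at 160 enrolled and roughly 2:1. Narrowing the scope alone would leave a figure based on 80 per group, whereas step 5 above gives 0.71 to 0.84 depending on attrition. Then add, for utilization, the detectable difference or expected confidence-interval width under stated assumed rates. For example, with risks of 20% and 10%, the 95% interval for the risk difference is about ±11 percentage points at 80:80 (1.96 × 0.0559) and about ±13 at 91:45 (1.96 × √(0.20 × 0.80/45 + 0.10 × 0.90/91) = 1.96 × 0.0674).

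**Section 4, Aim 2.** Keep the utilization measures where they are. Report them as risk differences and rate ratios with 95% confidence intervals. State that the trial was not powered on them, so a non-significant result is not evidence of no effect.

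**Cost.** Wording and a short calculation, with no change to enrolment, data collection or the endpoint hierarchy. The price is a less favourable stated power and a weaker claim for the utilization part of Aim 2.

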FCG Preparedness for caregiving is measured at baseline by the 8-item **Preparedness scale of the Family Care Inventory** which assesses the perceived level of preparation for various facets of caregiving such as dealing with physical needs and emotional problems. A five-point Likert-type scale is used ranging from 0 (not at all prepared) to 4 (very well prepared). The scale also assesses previous caregiving experience. Construct validity is shown through negative correlations between preparedness and caregiver worry and Cronbach alpha values range from 0.88 to 0.93(Archbold, Stewart, Greenlick, & Harvath, 1990; Schumacher et al., 2008).

FCG Relationship Quality will be measured using a modified, 4-item version of the Couples Satisfaction Inventory (CSI-4) (Funk & Rogge, 2007) at baseline, F1, and F2.

FCG general health, satisfaction with relationships and ability to carry out social activities will be measured using 3 items from the Patient-Reported Outcomes Measurement Information System (PROMIS-10) (David Cella et al., 2007) at baseline, F1, and F2.

FCG Somatic symptoms will be assessed at baseline, F1, and F2 using the Brief Symptom Inventory (BSI-18) somatic symptoms subscale (Derogatis & Spencer, 1993).

Positive and negative emotions will be assessed at baseline, F1, and F2 using a modification of the Positive and Negative Affect Schedule (Watson, Clark, & Tellegen, 1988). The four items we include are: stressed, in-control, frustrated and hopeful.

For FCGs whose patient passes away during the study period, the TRIG (Texas Revised Inventory of Grief Items)(Faschingbauer, 1981) will be used at all subsequent points to assess cognition, affect and behaviors associated with **bereavement**. Only the 13-item Present Grief section will be used. Likert-type scale with responses from "completely false" to "completely true."

Patient Well-Being

Patient distress will be assessed using the GAD-7 and PHQ-8 at baseline and F2 (see above).

Patient relationship quality will be assessed at baseline and F2 using a modified 4-item version of the Couples Satisfaction Index (see above).

Health Care Utilization

FCG health care utilization Participants will also be asked for self-reported health care utilization,

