primarily use path analysis to identify key mechanisms of the intervention on the outcome variable(s) at the 4- and 8-week assessment among the FCGs. The 80 participants in the intervention group will provide the primary data for these analyses, with additional data from participants in the waitlist control group who complete these assessments. It is expected that at least 50% in this group will provide data. Therefore, the expected sample size for the exploratory analyses will be at least 120.

Preliminary analysis: Basic descriptive analyses will be conducted. Chi-square and t-tests will be conducted to determine if the intervention (eSNAP + Caregiver Navigator; both randomized and non-randomized groups) or waitlist control groups significantly differ on demographics, patient medical characteristics, or outcome measures at baseline. Any measure with a group differences of $p < .10$ will be controlled for in primary analyses. Group differences and predictors of attrition will be examined using logistic regression. These results will be used to guide interpretation of primary analyses.

Aim 1 is to assess the preliminary efficacy of eSNAP + Navigator support intervention on FCG well-being. The hypothesis (FCG burden and distress at 8 weeks is lower for intervention group) can be most simply evaluated using independent-samples t-tests if randomization is fully successful. However, Generalized Estimating Equations (GEE) will be used to test the effects of the intervention at F1 and F2 in models that also include the baseline measure of the outcome variable and, if necessary, potential confounds determined by preliminary analyses. This approach handles missing data under the Missing At Random (MAR) assumption and permits analyses beyond those focusing on the outcome variable at 8 weeks (e.g. determining if intervention has an early impact or if effect matures over time). The primary test will be a planned contrast of the 2 conditions at the 8-week assessment within the entire model. The GEE will also assess (1) intervention differences in the primary outcome averaged across the 4 and 8 week assessments, (2) change from 4 to 8 weeks, and (3) group differences in change over time (intervention by time interaction term in the model).

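### By estimate, about half of the intervention arm was assigned without randomisation after amendment V11, and no planned Aim 1 or Aim 2 analysis separates it from the randomised comparison

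*Combined protocol and SAP*

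**What the plan says.** Section 3a states openly that randomisation stopped after V11, that everyone enrolled since then receives the intervention, and that a final ratio of roughly 2:1 is expected. Section 3b repeats the single assignment but still labels the design a two-group randomised controlled trial. Section 4, under the effect of the modified design, says the new accrual target leaves the analyses unchanged and concedes only that differences may be harder to detect.

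The preliminary analysis asks whether "the intervention (eSNAP + Caregiver Navigator; both randomized and non-randomized groups) or waitlist control groups significantly differ" at baseline, and adds: "Any measure with a group differences of $p < .10$ will be controlled for in primary analyses". For Aim 1, a GEE over F1 and F2 is fitted "in models that also include the baseline measure of the outcome variable". "The primary test will be a planned contrast of the 2 conditions at the 8-week assessment within the entire model". The same model also examines "group differences in change over time (intervention by time interaction term in the model"). For Aim 2, "For well-being, the simplest test of the hypothesis is an independent samples t-test", with a fallback: "If preliminary analyses show that randomization was not fully successful, then linear regression will be used". A patient baseline score is available for that regression: "Patient distress will be assessed using the GAD-7 and PHQ-8 at baseline and F2". Utilisation is analysed by two-stage and/or Poisson regression.

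Section 4 also plans a logistic regression of attrition to guide interpretation, and relies on the GEE to handle missing data under a missing-at-random assumption.

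**The concern.** All waitlist controls were enrolled while randomisation was running. By estimate, half of the intervention arm was enrolled afterwards. Any difference between the two periods in case mix, care, recruitment or data collection therefore falls on one side of the comparison only. Section 3a explains that blocks of 8 were used to keep the conditions balanced over time. V11 removed that protection, and no analysis takes its place. Section 3a also records one procedural change made with V11: the 6-month and 1-year assessments were dropped so that effort could go into retention and week-8 data collection.

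At stake is how the main result of both aims can be read. A pooled contrast presented under a randomised-trial label would be taken as randomised evidence when about a third of all dyads were never randomised. If the choice between pooled and randomised-only results is left until the data are seen, it is open to selection.

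**Working it through.** **Plan's own figures.** Section 4 gives 80 per group, d=0.5, two-sided alpha .05 and power of at least .80. The noncentral t gives 0.88, so the statement is correct. The accrual chain also holds: 300 × 0.75 = 225, and 225 × 0.85 × 0.85 = 162.6 against the stated 160. From these figures I take only that allocation before V11 was 1:1, which the documents imply but do not state.

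**Non-randomised share.** Inputs from section 3a: 160 dyads at about 2:1.
- Waitlist: 160/3 ≈ 53. Intervention: 160 − 53 ≈ 107. Randomised to intervention under 1:1: about 53. Not randomised: about 53.
- For a final ratio R:1 the share of the intervention arm is (R − 1)/R: 43% at R=1.75, 50% at R=2, 56% at R=2.25.
- Non-randomised share of all dyads: 53/160, about one third.

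**Completers.** Section 3b gives a current retention rate of about 85%, and 15% attrition at each of two follow-ups (0.85² = 0.7225). The pooled comparison is then about 91:45 or 77:39. The randomised-only comparison is about 45 or 38 per arm.

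**Bias.** Let D be the period difference in SD units and r the correlation of baseline with week-8 score. Neither is in the documents.
- Drift not reflected in the baseline score: the intervention mean shifts by share × D ≈ D/2.
- Drift fully carried by the baseline score, Aim 1 only: adjustment removes r × D/2 and leaves D(1 − r)/2, that is 0.30D, 0.20D and 0.10D at r=0.4, 0.6 and 0.8.

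**Aim 1 type I error at D=0.3.** SE = √(1 − r²) × √(1/n₁ + 1/n₂), with noncentrality bias/SE. For example, at r=0.6 and 77:39, SE = 0.8 × 0.1965 = 0.157 and 0.15/0.157 = 0.95, which gives 0.157.

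| r | Baseline-carried, 77:39 / 91:45 | Post-baseline, 77:39 / 91:45 |
|---|---|---|
| 0.4 | 0.079 / 0.083 | 0.131 / 0.145 |
| 0.6 | 0.067 / 0.069 | 0.157 / 0.175 |
| 0.8 | 0.057 / 0.059 | 0.243 / 0.275 |

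Over D at r=0.6, baseline-carried drift gives about 5%, 6%, 7% and 10% at D=0.1, 0.2, 0.3 and 0.5. Post-baseline drift gives about 6%, 10%, 16–17.5% and 35–40%.

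**The p<.10 screen.** At 107:53 it flags a 0.15 SD arm gap in a baseline measure about 23% of the time and a 0.25 SD gap about 44%.

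**Aim 2 well-being (illustrative).** A simulation of the t-test-or-regression procedure (12,000 runs per cell) gives about 4% with no drift. At D=0.3 it gives about 7% for baseline drift and 11–12% for later drift. It screens only the patient's own baseline score, whereas the plan also screens demographics and medical characteristics. Utilisation is not quantified.

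**What a period term does.** In a GEE simulation at r=0.6 (5,000 runs) with 0.3 SD drift at F2 only, the pooled week-8 bias is 0.15 SD. A period main effect alone leaves about 0.075; period plus period-by-time leaves −0.001, the same as randomised-only.

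**The case against.** The plan is not without protection. It puts the baseline outcome in the Aim 1 model, screens demographics, medical characteristics and baseline outcomes for covariates, examines predictors of attrition, and relies on a model intended to cope with data missing at random. The one documented procedural change, effort moved to week-8 retention, acts first on who is missing, which the attrition analysis looks at. The funder approved the redesign, and the aims are worded as preliminary efficacy. All of this stands, and case-mix drift visible at baseline may be caught. None of it separates the periods or removes drift that measured baseline variables do not reflect. Section 4 also ties the softer wording of the aims to lower power, not to lost comparability.

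A reader might infer three stronger things that the documents do not support. First, that the effect estimate is in fact biased: no passage reports any shift between periods, and D is hypothetical. Second, that half of any period difference enters the estimate: a factor that already shows in the baseline score is partly removed in Aim 1. Third, that pooling must be abandoned: the pooled contrast is more precise, and which contrast leads is partly a trade-off.

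**Conclusion.** The omission is real and affects the primary contrast of both aims. About half of the intervention arm (43–56%) has no concurrent controls, and no planned Aim 1 or Aim 2 analysis isolates the randomised comparison or tests how far the result depends on the later enrolees. The explicit pooling is in the baseline comparison. The population of the week-8 test is not stated separately, but nothing restricts it.

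The size depends on drift that nobody has reported. The potential bias is about D/2 for drift outside the baseline score and D(1 − r)/2 in Aim 1 for drift fully inside it. At D=0.3 that means an Aim 1 type I error of about 6–8% or 13–28% over r=0.4–0.8. The conclusion rests on the inferred 1:1 allocation, the approximate 2:1 ratio, and assumed D and r. The need to prespecify the randomised comparison does not depend on any particular D.

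**What to change.** - For Aims 1 and 2, prespecify a comparison among participants randomised before V11. An equivalent is a model on all participants with an enrolment-period term, plus period-by-time in the Aim 1 F1/F2 GEE. A period main effect alone is not enough there if drift differs between F1 and F2.
- Report it beside the pooled contrast, and label the pooled contrast as partly non-randomised. Rest any claim of randomised evidence of efficacy on the randomised comparison.
- State before analysis which contrast leads. That choice is the sponsor's.
- In section 3b, describe the design as randomised until V11 and single-assignment afterwards.
- Keep the non-randomised participants in Aim 3.

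No new data are needed, only wording and model specification. The price is precision. At d=0.5, randomised-only power is about 0.58 or 0.65 unadjusted (38 or 45 per arm), against 0.71 or 0.78 pooled (77:39 or 91:45). With an assumed r=0.6 it is 0.77 or 0.83 against 0.88 or 0.93. The period-by-time model gives about 0.77 or 0.83, so it recovers almost nothing over randomised-only. Aim 2 patient self-report may have fewer participants still, because caregivers can enrol without a consenting patient.
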